In summary, SNRB, despite utilized frequently in the diagnostic work-up with patients with lumbar radiculopathy, vary widely in their sensitivity and specificity. The reasons, as outlined above, are multifactorial. The proposed study aims to minimize the known limitations of these injections and prospectively define their positive and negative predictive value in a homogenous group of patients undergoing surgery for lumbar foraminal stenosis and radiculopathy. The design will define a threshold of response utilizing both subjective and objective measures and more accurately predict excellent results following surgery.

Scientific Approach

Patients, age 18-80, who present with unilateral lower extremity radiculopathy due to degenerative foraminal stenosis will be considered for this study. Patients will be included if they present with radiculopathy and with imaging and/or clinical history or physical exam that does not demonstrate a clear neurogenic source of their pain. Examples include MRI with multi-level foraminal stenosis or discordance between MRI and clinical radiculopathy. All patients enrolled in the study will undergo a SNRB of the suspected symptomatic nerve root. Patients will undergo lumbar foraminotomy regardless of the response to the injection.

Patients will be excluded if there is a clear correlation between imaging and radiculopathy. An example would be an L5 radiculopathy in the face of an acute L4/5 herniated disc. Additional exclusion criteria include: radiculopathy associated with trauma, tumor or infection. Non-radicular lower extremity pain will also be excluded. Patients who cannot tolerate the SNRB without IV sedation will not be enrolled.

Subjects must be available for the entire study duration (12 months) and willing and able to comply with scheduled visits including completing pain diary and all patient reported outcome questionnaires.

Patients will be contacted by phone during the study follow-up (48 hours post injection).

Other exclusion criteria:

Surgery requiring multi-level decompression and/or fusion

Surgical indication for malignancy, injection or acute or emergency trauma

History of major surgery within 3 months prior to enrollment

Pregnant females

Presence of severe acute, chronic medical or psychiatric condition

Patients meeting inclusion criteria and following signing of the informed consent will undergo SNRB prior to surgery. **The surgeon will be blinded to the**

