response to the injection. Patients will proceed to surgery regardless of their response to injection.

Description of Procedures

1. Pre-Injection Pain and Functional Assessment

Prior to the injection the patient will report pain and functional status via tablet. Outcome measures recorded include VAS leg pain, ODI, PDQ and EQ-5D.

Patients will perform a 30-meter walk test. For this test, the patient will start from a sitting position. When begun, the patient will rise and walk a pre-measured and level 30 meters. The time to conduct the test as well as a count of cadence will be performed by the research coordinator. A post walk VAS leg pain will be recorded immediately following the walk test.

2. Selective Nerve Root Block

A single interventionalist in an ambulatory surgical center will perform all injections. Injections will be performed utilizing biplanar fluoroscopy to appropriately localize the foramen of interest and optimal needle placement. Patients will not be administered IV analgesic or anxiolytic medications. After prone positioning, the skin in the lumbar region of interest will be prepped and draped per hospital protocol. One milliliter of 1% lidocaine will be injected as a wheel into the skin in the planned incision. The injection needle will then be inserted into the anterosuperior aspect of the foramen via biplanar fluoroscopy. After confirmation of appropriate placement, 0.5 milliliters of nonionic contrast will be injected and a "radiculogram" confirmed. Epidural spread or vascular uptake of contrast will require abortion of the injection. The patient will be rescheduled for one week later for a repeat injection attempt. Inability to perform an adequate injection (i.e., lack of epidural spread) will result in exclusion of the patient from the study. To be confirmed accurate the injection should replicate the patient's presenting radicular pain. 0.3 milliliters of 0.5% bupivacaine will then be injected into the foramen. The patient's response to injection will be recorded: did the injection of contrast replicate the patient's pain; did the injection of bupivacaine result in both motor and sensory changes associated with the nerve injected? Adequacy of injections (i.e., needle location and contrast spread) will be reviewed by a third party (saved fluoroscopic images).

3. Post Injection Pain and Functional Assessments

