Following recovery of the injection, the patient will report a post-injection VAS leg pain score. The patient will then perform a post injection 30-meter walk test. Time and cadence count will be recorded as well as post walk test VAS leg pain. Patients will resume normal activities and given a pain diary.

4. 48 Hour Post Injection Assessment

At 48 hours post injection, all patients will be called. A 48-hour VAS leg pain will be assessed and pain diary reviewed. The duration of pain

change will be recorded. The change will be based on the minutes elapsed since pain improved post injection and the number of hours it took to return back to baseline.

5. Lumbar Foraminotomy

All operations will be performed at the main campus Cleveland Clinic by a fellowship trained spine surgeon. After induction of general anesthesia and patient positioning, the lumbar skin will be prepped and draped per hospital protocol. A preoperative lateral radiograph will confirm the level of incision. The smallest incision possible will be made and subperiosteal exposure utilized to expose the level of foraminotomy. The spinous process is next resected and a laminotomy performed on the index ipsilateral side. Following medial facetectomy, Kerrison Rongeurs will be utilized to remove overgrown bone and ligamentum flavum to decompress the neural foramen. Discectomy may be required to fully decompress the existing nerve root. The easy passage of a Woodson elevator through the foramen will be utilized to confirm adequate opening of the foramen.

6. Following surgery all patients will be seen at 6 weeks, 3, 6 and 12 months.

During follow-up, patient reported outcomes will be recorded including VAS leg, ODI, PDQ and EQ-5D. Any adverse events will be recorded and noted associated or not associated with the index operation. **Any patient without improvement in symptoms 3 months post surgery will undergo MRI to assess adequacy of foraminal decompression.**

7. An excellent surgical outcome will be defined as 15-point improvement in ODI, 26 point improvement in PDQ, improvement in VAS leg pain to 0-2, and improvement in quality of life per EQ5D.

Statistical Analysis

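### The only adverse-event rule sits at the post-surgery visits and tests causality only against the operation, so harms of the nerve root block risk being unrecorded or misclassified

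*Combined protocol and SAP*

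**What the plan says.** In the Combined protocol and SAP, adverse events are covered by one sentence in Description of Procedures, item 6: "Any adverse events will be recorded and noted associated or not associated with the index operation". That item opens with the visit schedule: "Following surgery all patients will be seen at 6 weeks, 3, 6 and 12 months".

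Exposure to the block comes earlier and is universal. Scientific Approach states: "All patients enrolled in the study will undergo a SNRB of the suspected symptomatic nerve root". The items that cover the block period collect other data:

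- Item 2, at the injection: "The patient's response to injection will be recorded: did the injection of contrast replicate the patient's pain", and whether the anaesthetic produced motor and sensory change.
- Item 3, after the injection: leg-pain VAS, walk time and cadence.
- Item 4, the 48-hour call: "A 48-hour VAS leg pain will be assessed and pain diary reviewed", plus the duration of the pain change.

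Item 2 also provides for failed injections. "Epidural spread or vascular uptake of contrast will require abortion of the injection", with a repeat attempt a week later. Inability to achieve an adequate injection "will result in exclusion of the patient from the study".

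The Statistical Analysis section contains no safety summary.

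**The concern.** The block is the procedure whose diagnostic value is being studied, but the harm rule is built around the other procedure, in two respects.

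The first is the collection window. The rule is placed in follow-up after surgery, where the first scheduled visit is at 6 weeks. A patient who leaves the study because the injection could not be done adequately has had a needle inserted, possibly twice, and has no scheduled contact at which the rule applies.

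The second is attribution. The only causality question is whether the event is related to the index operation. A block harm reported at follow-up can be answered no, which puts it with events unrelated to either procedure, or yes, which counts it as a surgical harm. Neither answer identifies it as a harm of the block.

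At stake is whether the pilot can state a usable block-harm rate with a clear denominator before the same kind of injection is taken into a larger multicentre study.

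**Working it through.** The documents state no safety figure, and the sample of 50 has no power derivation, so there is no planned number to reproduce. The check is a comparison of the text, with a calculation for scale.

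**Text, step by step (Description of Procedures)**

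| Step | What is collected | Adverse-event item? | Causality categories |
|---|---|---|---|
| Item 2, injection | Pain replication, motor and sensory change | None | None |
| Item 3, post-injection | Leg-pain VAS, walk time, cadence | None | None |
| Item 4, 48-hour call | Leg-pain VAS, diary, duration of change | None | None |
| Item 6, visits from 6 weeks after surgery | Patient-reported outcomes, any adverse event | Yes | Related or not related to the operation |

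Two patient paths follow.

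1. *Excluded after an inadequate injection.* The patient passes through item 2 and leaves before surgery. Item 6 is never reached, so no written rule records a harm of the attempt.
2. *Block completed, then surgery.* Item 6 is reached. A harm of the block is entered as related to the operation (wrong cause) or not related (mixed with unrelated events). No onset date is required that would help separate the two later.

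**Scale (assumed rates; the documents give none)**

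Inputs: n = 50, the enrolment target in Statistical Analysis, taken as the number exposed; p = the assumed proportion of patients with a block event; patients independent; full capture.

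Expected patients with an event = 50 × p. Chance of at least one = 1 − (1 − p)^50.

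| p | Expected | Chance of at least one |
|---|---|---|
| 0.5% | 50 × 0.005 = 0.25 | 1 − 0.995^50 = 22% |
| 1% | 50 × 0.01 = 0.5 | 1 − 0.99^50 = 39% |
| 2% | 50 × 0.02 = 1.0 | 1 − 0.98^50 = 64% |
| 5% | 50 × 0.05 = 2.5 | 1 − 0.95^50 = 92% |

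If none were seen in 50 fully observed patients, the one-sided 95% upper bound would be 1 − 0.05^(1/50) = 5.8% (two-sided exact: 1 − 0.025^(1/50) = 7.1%).

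The expected count is therefore between a quarter of an event and two and a half. Losing or mislabelling one or two events would remove most of what the pilot could say about block safety. The 5.8% bound is valid only if every needle-exposed patient was asked, which the present text does not ensure.

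**The case against.** The case on the other side corrects several tempting inferences.

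- *A reader might infer that the pilot must report zero block harm.* The text does not support that. The rule covers any adverse event and allows it to be classed as unrelated to the operation, so a block harm can be recorded and described. Staff may also note a harm informally at the 48-hour call, and Aim 1 says all injected patients are called. What stands is that no step tells anyone to ask, and no category identifies the block as the cause.
- *A reader might count motor or sensory change, or contrast in a vessel, as harms.* Item 2 records the former as part of the response to the block, and treats the latter as a technical reason to abort. No injury is described in either case.
- *A reader might say that vascular uptake leads straight to exclusion.* It leads first to a second attempt. The exclusion sentence concerns inability to achieve an adequate injection, and its parenthesis gives lack of epidural spread as the reason, although epidural spread is itself a ground for aborting. Those sentences need reconciling. On any reading, though, some patients can be excluded after a needle has been inserted.
- *A reader might infer that intolerant patients are exposed and then erased*, from "Patients who cannot tolerate the SNRB without IV sedation will not be enrolled". This is an eligibility criterion that may be applied at screening, before any needle. Needing sedation is also not in itself an adverse event.
- *A reader might say that the blinded surgeon will misattribute a persisting deficit.* No assessor of causality is named, and the duration of the blinding is not given. The dated observations before surgery could help to separate the two causes.

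It is also fair that both aims concern predictive value and threshold, that the stated uses of the pilot data do not include safety, and that consent pages are not in the supplied file, so reporting instructions there cannot be excluded. None of this supplies the missing collection step or causality field in the protocol text.

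**Conclusion.** The concern holds as a gap in when harms are collected and how they are attributed. As written, block harms risk being unrecorded in patients excluded after an inadequate injection. In the rest, they risk being pooled with unrelated events or credited to surgery. This is a risk created by the text, not a certainty. The predictive values and the threshold analysis are unaffected, so this is a change that should be made rather than a flaw in the main result.

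The size cannot be fixed from the documents. The 22% to 92% chance of at least one event rests on assumed rates of 0.5% to 5%, on 50 exposed patients and on independence between patients, and serves only for scale. The textual finding depends on none of these assumptions. It is limited to the protocol text supplied.

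**What to change.** 1. Record adverse events from first needle insertion for every consented patient, including those whose injection is aborted, repeated or fails, and those then excluded.
2. Add an adverse-event question to the post-injection assessment and to the 48-hour call.
3. Replace the single causality item with two separate fields, relatedness to the SNRB and relatedness to the index operation, each event with an onset date.
4. Add a descriptive safety summary that reports block and surgical events separately, with everyone who had a needle inserted as the denominator for block events.

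None of this alters the injection, the surgery or the predictive analysis. Collection uses contacts that already exist. The cost is slightly more data entry, a few case-report-form fields, a defined safety population, and keeping excluded patients in the adverse-event record. The reported block-event rate may look less favourable than under the present rule.

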To improve the diagnostic value of SNRB, a threshold between positive and negative responses will be set that is best able to predict whether a patient will have a good surgical outcome. To measure the response to injection, post-injection VAS pain scores and functional assessments will be compared to pre-injection values for each patient.

First, the functional and VAS pain measures of improvement will be analyzed individually. A positive functional response to injection will be defined by setting thresholds in the timed 30-meter walk test that best differentiates patients who respond to surgery from those who do not. The accuracy of the test will be defined by its sensitivity and specificity and by its negative and positive predictive values. Separately, a threshold defining a positive response to injection will be set using VAS leg pain improvements over pre-injection values.

Then, a logistic regression analysis will be performed, including pain assessments and walk test improvements as predictors. This model will assign a value between 0 and 1 that represents how likely it is that a patient who responds to SNRB with some amount of reduction in leg pain and improvement in

[name]

Threshold Response of Selective Nerve Root Block

functional ability has a good surgical outcome. A threshold in the model's predictive values will be set to define a positive response to the injection. This will again be done to maximize its diagnostic accuracy with respect to sensitivity and specificity and to positive and negative predictive values.

Positive and negative predictive values and their 95% confidence intervals will be reported both for the individual analyses and for the combined logistic regression analysis. Lastly, variable selection will be performed in an attempt to simplify the logistic regression model.

Due to the fact that a threshold response to SNRB has not been studied, we are not able to perform an adequate power analysis. We will use the data from this pilot study to perform a power analysis for a planned larger randomized trial. To have an adequate sample yet complete the study in a 12 month time period we plan to enroll 50 patients.

Plans for Dissemination of Results

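### With no ODI or PDQ minimum at entry, a patient starting below 15 ODI or 26 PDQ points fails the item 7 outcome whatever surgery achieves

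*Combined protocol and SAP*

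**What the plan says.** **Entry.** Scientific Approach opens with "Patients, age 18-80, who present with unilateral lower extremity radiculopathy due to degenerative foraminal stenosis will be considered for this study" and continues "Patients will be included if they present with radiculopathy" without a clear source on imaging, history or examination. Neither the inclusion nor the exclusion criteria give a minimum for leg pain, ODI, PDQ, EQ-5D or walking.

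**Baseline.** Item 1 of Description of Procedures collects the scores before the injection: "Outcome measures recorded include VAS leg pain, ODI, PDQ and EQ-5D". They are not used for eligibility.

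**Outcome.** Item 7 asks for "15-point improvement in ODI, 26 point improvement in PDQ, improvement in VAS leg pain to 0-2" and adds "and improvement in quality of life per EQ5D". The components are joined by *and*, so the natural reading is that all four are required.

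**Test.** Under Statistical Analysis, block response is a within-patient change: "post-injection VAS pain scores and functional assessments will be compared to pre-injection values for each patient". For pain, "a threshold defining a positive response to injection will be set using VAS leg pain improvements over pre-injection values". For walking, a positive response comes from "setting thresholds in the timed 30-meter walk test that best differentiates patients who respond to surgery from those who do not". No cut-off is fixed, and the plan does not say whether pain change is absolute or percentage. The logistic model lists pain and walk-test measures as predictors; baseline ODI and PDQ are not among them.

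No rule covers a patient whose starting score puts an outcome component out of reach.

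**The concern.** Two of the four outcome components are fixed-size gains, and the plan does not check that every patient has room to make them. A failure that follows from the starting score says nothing about whether the block found the right root or whether the decompression worked. It still enters the two-by-two table as if it did.

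The direction of the error depends on the block result. A forced failure in a block-positive patient is a false positive and lowers PPV (and specificity). In a block-negative patient it is a true negative and raises NPV and specificity. PPV and NPV are the subject of Aim 1. The response cut-offs are chosen to separate surgical responders from non-responders in the same data, so forced failures also sit in the group that the threshold is tuned to identify. The protocol intends to carry that threshold, and the power inputs, into a larger study.

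**Working it through.** **1. Room to improve.** Assumption: ODI, PDQ and VAS all have a lowest score of 0, so the largest possible gain equals the baseline.

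- ODI: a 15-point gain is possible only if baseline ≥ 15. At 14 it is impossible; at 15 the patient must reach 0.
- PDQ: a 26-point gain is possible only if baseline ≥ 26. At 25 it is impossible; at 26 the patient must reach 0.
- Leg VAS: this component is an end state reached by improvement, not a fixed gain. On a 0–10 integer scale every baseline from 1 to 10 can improve to a value in 0–2; only 0 cannot. A low starting VAS makes this component easier.

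The forced failure therefore comes from ODI and PDQ.

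**2. Illustrative starting table.** The plan gives no expected table and no power calculation for its 50 patients, so there is no figure of its own to reproduce. I use the retrospective series of 100 consecutive patients described in Background and significance: block-positive, 41 good and 10 not; block-negative, 6 good, 2 not and 1 lost. The quoted accuracy figures are recovered if the lost patient counts as a good outcome: PPV 41/51 = 80.4%, NPV 2/9 = 22.2%, sensitivity 41/48 = 85.4%, specificity 2/12 = 16.7%. Leaving the lost patient out gives 59 patients and NPV 2/8 = 25.0%, used below.

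**3. Putting k forced failures into 50 patients.** The other 50 − k follow the proportions 41, 10, 6 and 2 out of 59. With r = (50 − k)/59:

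- all k block-positive: PPV = 41r / (51r + k); NPV unchanged
- all k block-negative: NPV = (2r + k) / (8r + k); specificity = (2r + k) / (12r + k); PPV unchanged
- k block-positive in the same proportion as the rest (51/59): PPV = 80.4% × (1 − k/50); NPV = 1 − 0.75 × (1 − k/50)

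| k | PPV, all positive | NPV, all negative | Specificity, all negative | PPV, same proportion | NPV, same proportion |
|---|---|---|---|---|---|
| 0 | 80.4% | 25.0% | 16.7% | 80.4% | 25.0% |
| 1 | 78.5% | 34.8% | 24.3% | 78.8% | 26.5% |
| 3 | 74.9% | 49.0% | 36.6% | 75.6% | 29.5% |
| 5 | 71.2% | 58.8% | 46.1% | 72.4% | 32.5% |

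Example, k = 3: r = 47/59 = 0.797. PPV = 32.7/(40.6 + 3) = 74.9%; NPV = (1.6 + 3)/(6.4 + 3) = 49.0%. NPV moves most because the block-negative group is small: 8 × 50/59, about 7 patients.

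The values of k are chosen, not sourced. The series' outcome was symptom relief rather than item 7, and the table holds block classification fixed although the plan would refit the cut-off.

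**4. Are forced failures also block-negative?** Not necessarily. Block status comes from leg VAS and walk time, not ODI or PDQ. A simulation assumed mean VAS 5–7 (SD 2), ODI 30–45 (SD 16), PDQ 50–80 (SD 28) and between-scale correlation 0.6, with block response independent of surgical response. Among patients who could not meet the outcome (including those with VAS 0), 60–73% still had a VAS drop of at least 2 after the block; at correlation 0.3, in the middle scenario, it was 76%. These shares depend on the assumed block response and show only that both cells are possible.

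**The case against.** **Item 7 may not be the endpoint.** It defines an excellent outcome, whereas Statistical Analysis speaks of a good outcome and Aim 2 of meaningful leg-pain improvement, which an ODI or PDQ floor does not block. This stands as a condition on the point. Item 7 is, however, the only outcome definition in the documents, and the aims and the Background summary both name excellent results as the target.

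**Few patients may be affected.** Everyone enrolled has radiculopathy and is going to surgery, so very low disability scores may be rare. This stands; no baseline distribution is given.

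**The shifts are within sampling error.** The exact 95% interval for 2/8 is about 3% to 65%, and a PPV of 80% in some 43 block-positive patients carries about ±12 points (1.96 × √(0.8 × 0.2/43)). True for a pilot. But the intervals do not account for this error, and a larger study with the same rules would inherit it.

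**Two stronger readings are tempting.** A reader might infer that low-baseline patients are true negatives by construction. The documents do not support that: a patient with low ODI or PDQ can have high leg VAS or a slow walk and respond to the block. A forced negative test would need low VAS, an absolute-change cut-off and no walk response, and the plan has fixed no cut-off. A reader might also infer that a leg VAS of 2 or less at entry rules out success. It does not, since a patient at 1 or 2 can still improve within the 0–2 range.

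**A floor does not cure everything.** Patients just above 15 or 26 must improve almost to zero, and EQ-5D also needs room to rise. Both stand as limits of the remedy.

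**Conclusion.** The point holds for ODI and PDQ. Scientific Approach has no floor, item 7 requires fixed gains on both scales, and no handling rule exists, so a patient below 15 or 26 points is an outcome failure from the start. This rests on three assumptions: both scales bottom out at 0, all four components are required, and item 7 is the reference standard.

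The size is unknown. On the cited series' proportions, one to five such patients in 50 would lower PPV by about 2 to 9 points if all were block-positive, or raise NPV by about 10 to 34 points if all were block-negative. If they were spread like the rest, PPV would fall by about 2 to 8 points and NPV rise by about 2 to 8. These figures are illustrations, not forecasts. It is an inexpensive improvement worth making before the data are analysed.

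**What to change.** State that item 7 is the reference standard for the predictive values. Then, using the pre-injection scores already collected, take one of two routes:

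- **Eligibility:** require ODI of at least 15 and PDQ of at least 26 at entry. As written, the scores are taken after consent, so some patients would become post-consent screen failures.
- **Analysis set:** leave eligibility unchanged and pre-specify that the main two-by-two tables and the threshold analysis use patients for whom the ODI and PDQ components are attainable. Report how many were removed, and give the full-cohort result as a sensitivity analysis.

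The second route changes no patient's care, and because it depends only on pre-injection data it cannot be steered by block response or outcome. No leg VAS minimum is needed for attainability. It would also help to state whether VAS response is absolute or percentage change.

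The cost is one eligibility line or one analysis-set rule. A few low-disability patients are screened out or left out of the main table, which slightly narrows the population and the sample, and patients just above the floors still have little room to succeed.
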